2.5 Study Design

This is a phase 2-3 study with a total of 200 participants with newly-diagnosed intermediate or high-risk prostate cancer scheduled to undergo prostatectomy and lymph node dissection. Eligible participants will undergo baseline assessments at enrollment. Study participants will receive ^{68}Ga -PSMA-11 and undergo a PET/MRI. All patients will first be seen by a Stanford Cancer Institute physician (Drs [name], [name], [name] and [name]) who will refer patients if appropriate on clinical grounds to Dr [name] or his colleagues for this study. The following steps will take place.

1. After signed the informed consent document, participants will be given a copy of the signed form.
2. Participant will be asked to drink 1 to 2 glasses of water before arrival at the clinic
3. Participants will be weighed and vital signs (heart rate and blood pressure) will be recorded
4. Study personnel (eg, technologist) will verify subject identify; radiopharmaceutical identity; dose; and administration route. Participant will be injected IV with 3 to 7 mCi of ^{68}Ga -PSMA-11
5. Participant will void immediately prior to the scan

6. Approximately 50 to 100 minutes after the radiopharmaceutical IV administration, data acquisition will begin in the pelvic region and move toward the head. First, localizer MRI scans will be performed to define the table positions. After correct positioning of the spatial acquisition windows is ensured, the combined PET/MRI acquisition will be initiated with 3 to 5 table positions at a 4-min acquisition time per table position.
7. Vital signs (heart rate and blood pressure) will be recorded again at the completion of the study.
8. Participants will be dismissed.
9. Participants will be contacted at 24 to 72 hours following the scan in order to capture potential late occurring Adverse Events.

The ^{68}Ga -PSMA-11 PET/MRI may be repeated at the completion of treatment to evaluate response to therapy, if requested by the treating physician.

Objectives of the Study

Primary

- Sensitivity, specificity, positive and negative predictive value of ^{68}Ga -PSMA-11 PET/MRI for the detection of regional nodal metastases compared to pathology at radical prostatectomy on a per patient basis using nodal regional correlation.

Secondary

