5.3 Image interpretation

1. ^{68}Ga -PSMA-11 PET

PET images will initially be interpreted in random order at separate reading sessions by 3 board-certified nuclear medicine physicians. Cross-sectional MRI imaging from the PET will be available for anatomic correlate. Final reads for each patient will be interpreted as positive or negative for the presence of pelvic nodal disease, and positive or negative for the presence of osseous metastatic disease and soft tissue metastases outside of the pelvis.

Clinical Follow-up

- a. Prostatectomy: patients without evidence of PSMA-11 PET positive nodal or metastatic disease noted on imaging will undergo radical prostatectomy. If a PSMA-11 PET positive regional pelvic node is noted, the urologist will be informed of the location of the suspicious node and the patient will undergo prostatectomy with nodal dissection.
 - i. Patients with nodes seen on PSMA-11 PET without positive nodes on pathology, will be rescanned with CT or MRI to determine if the suspicious node was thought to be removed. A PSMA-11 PET may be repeated as well at the discretion of the treating physician.
- b. If sites of PSMA-11 PET positive osseous or distant metastatic lesions are noted, the urologist will be informed, and further evaluation including further imaging (bone scan; NaF PET; CT; or MRI cross-section imaging) or targeted biopsy will be performed in order to restage the patient prior to the decision regarding whether or not a prostatectomy will be performed as per the responsible surgeon and standard of clinical care.

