c) Analysis plan for Primary Aim 1: For this study to reach success, 2 out of the 3 readers will have to demonstrate a detection sensitivity of 65% or greater for nodal metastases. Additionally, 2 out of the 3 readers will have to demonstrate a detection specificity of 90% or greater for regional nodal metastases based upon region as defined below on a per patient level. The sensitivity, specificity, positive and negative predictive value of PSMA-11 PET for the detection on a per patient basis will be determined using the below criteria:

- i) True positive patient:
 - (1) PSMA-11 PET-positive for regional nodes; pathology at prostatectomy positive for regional nodes. Region will be defined by the granularity used by the urologist at time of prostatectomy. Sensitivity will be calculated at a patient level by region, meaning that one correct region would make a true positive on a patient level. Only one node needs to correspond between imaging and pathology for a patient to be considered a true positive.
 - (2) PSMA-11 PET-positive for regional nodes; pathology negative for regional nodes; imaging after prostatectomy demonstrates node was not removed at surgery; and follow-up biopsy or imaging demonstrates presence of nodal disease.
 - (a) Criteria for positive node on follow-up imaging: imaging within 3 to 12 months; the node decreases by more than 30% (for patients undergoing systemic treatment or focal therapy at this site); or increase by more than 20% in short axis diameter in the absence of treatment (with a minimum of 3 mm in change in size).
- ii) True negative patient:
 - (1) PSMA-11 PET-negative for regional nodes; pathology at prostatectomy negative for regional nodes.
- iii) False positive patient:
 - (1) PSMA-11 PET-positive for regional nodes; pathology at prostatectomy is negative; and imaging after prostatectomy demonstrates that node is no longer present.
 - (2) PSMA-11 PET positive for regional node, but pathology at prostatectomy is positive for node but in a different nodal region than that node seen on PSMA-11 PET.

iv) False negative patient:

- (1) PSMA-11 PET negative for regional nodes, but pathology at prostatectomy is positive.

v) Non-evaluable:

- (1) PSMA-11 PET positive for regional nodes; pathology negative for regional nodes; imaging after prostatectomy demonstrates node was not removed at surgery; and no definitive follow-up is available.

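### True-positive rule i(2) makes the reference standard depend on the PET read, so follow-up can raise each reader's sensitivity against the 65% cut-off but never lower it

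*Combined protocol and SAP*

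**What the plan says.** The primary objective (synopsis and section 2.5) is sensitivity, specificity, PPV and NPV for regional nodal metastases, "compared to pathology at radical prostatectomy on a per patient basis using nodal regional correlation". It has no follow-up component.

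Section 10.3.2 c) then classifies each patient:

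- **True positive, rule i(2):** PET positive, pathology negative, and "imaging after prostatectomy demonstrates node was not removed at surgery; and follow-up biopsy or imaging demonstrates presence of nodal disease". The imaging criterion begins "Criteria for positive node on follow-up imaging: imaging within 3 to 12 months" and requires a defined size change.
- **True negative, rule ii):** "PSMA-11 PET-negative for regional nodes; pathology at prostatectomy negative for regional nodes". No follow-up condition is attached.
- **False negative, rule iv):** "PSMA-11 PET negative for regional nodes, but pathology at prostatectomy is positive". This is the only route.
- **False positive, rule iii(1):** PET positive, "pathology at prostatectomy is negative; and imaging after prostatectomy demonstrates that node is no longer present".
- **Non-evaluable, rule v(1):** PET positive, pathology negative, "imaging after prostatectomy demonstrates node was not removed at surgery; and no definitive follow-up is available".

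Section 5.3 says who is re-imaged: "Patients with nodes seen on PSMA-11 PET without positive nodes on pathology, will be rescanned with CT or MRI". The study calendar in section 7 lists no follow-up imaging. Success requires at least 65% sensitivity in 2 of 3 readers and at least 90% specificity in 2 of 3 readers.

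**The concern.** Pathology cannot verify a node that was left in the patient, so some use of follow-up is understandable. Here, however, the index test decides who receives it. A retained diseased node that PET saw can be confirmed and credited to PET. A retained diseased node that PET missed is just as real, yet its owner is a true negative by definition. This is differential verification conditioned on the test under study.

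Because success is judged reader by reader, the definition also conflicts with itself. Take one pathology-negative man whose retained node is later proven diseased. He is a true positive for a reader who called him positive. For a reader who called him negative he is a true negative, and that reader gains specificity credit for a miss.

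At stake is a success criterion defined as a bare point estimate, which a very small number of patients can move across the line.

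**Working it through.** **Routes into the diseased group**

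| PET | Pathology | Later evidence | Class |
|---|---|---|---|
| + | - | node retained, disease shown | true positive, i(2) |
| + | - | node retained, nothing definitive | non-evaluable, v(1) |
| + | - | node gone | false positive, iii(1) |
| - | - | any | true negative, ii) |
| - | + | not needed | false negative, iv) |

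Only the first row lets follow-up change disease status, and it requires a positive PET.

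**Direction.** Let TP and FN be the counts among pathology-positive men and k the number of i(2) patients for one reader. Pathology-only sensitivity is TP/(TP+FN). The plan's figure is (TP+k)/(TP+FN+k). The difference is k x FN / [(TP+FN)(TP+FN+k)], which is never negative and is positive whenever k and FN are both above zero.

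**Number of diseased men.** Section 10.2.1 states that 61 are needed. That figure is reproduced by a one-sided, one-sample test of 65% against a fixed 45% at alpha 0.01 and 80% power: [(2.326 x sqrt(0.45 x 0.55) + 0.842 x sqrt(0.65 x 0.35)) / 0.20]^2 = 60.7, so 61. The same section's other inputs imply 200 x 0.75 x 0.30 = 45. That mismatch is a separate matter, so both values are used here.

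**Size for one reader.** The value of k is not in the documents and is assumed. Every pathology-positive man is taken to be a true positive or a false negative, with none under the wrong-region false-positive rule iii(2).

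- With 45: 29/45 = 64.4% fails; k = 1 gives 30/46 = 65.2%, a pass.
- With 61: 39/61 = 63.9% fails; k = 1 gives 40/62 = 64.5%, still a fail; k = 2 gives 41/63 = 65.1%, a pass.
- Further from the line, with 45: 27/45 = 60.0% becomes 30/48 = 62.5% with k = 3 and passes only at k = 7 (34/52 = 65.4%).

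**Chance of passing, one reader, 45 men, true pathology-based sensitivity 60%, k fixed.** The binomial probability of reaching 65% is 22.5% at k = 0 (30 or more of 45), 32.7% at k = 1 to 3 (29 or more) and 44.4% at k = 5 (28 or more).

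**Comparison with even-handed follow-up.** Suppose u pathology-negative men have residual disease and PET finds 60% of resected and residual disease alike. The rule reports (27 + 0.6u)/(45 + 0.6u): 61.0% at u = 2, 62.5% at u = 5 and 64.7% at u = 10. Pathology alone, or follow-up applied equally to all, gives 60.0% throughout.

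**Disagreement between readers.** Two readers each score 29/45, and one man has a retained node later proven diseased. The reader who called him positive moves to 30/46 = 65.2%. The reader who called him negative stays at 29/45 = 64.4%. With one disease status for that man, the second reader would have 29/46 = 63.0%.

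**Specificity.** The 45 leave 150 - 45 = 105 pathology-negative men. Suppose 12 are PET positive, two of them under i(2). The plan's specificity is 93/103 = 90.3%. Against pathology alone it is 93/105 = 88.6%.

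**The case against.** The case for rule i(2) is a fair one. It is prespecified, it addresses a real failure of pathology as a reference, and it sets a demanding test: negative pathology, a node shown to remain, and then a positive biopsy or a defined change in size (more than 30% shrinkage under treatment, or more than 20% growth without it, with a 3 mm minimum change). Section 5.3 also has the urologist told where the suspicious node lies, which should limit the number left behind. All of this bears on size and stands. None of it bears on direction, because prespecification does not remove a one-sided correction.

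Three stronger readings are tempting and are not supported:

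- **That the trial's verdict is likely to be reversed.** The counts above that cross 65% were found by solving for them, and they concern one reader. Two of three readers must pass, and the specificity criterion must be met as well.
- **That the paired comparison with conventional imaging is biased in the same way.** Section 10.3.4 bases per-patient sensitivity in that comparison on confirmation by histopathology or biopsy. Only biopsy-confirmed i(2) cases could enter it.
- **That PET-negative men are never followed.** Time to PSA progression is an exploratory endpoint in section 2.5. It does not feed the classification, which is the narrower point made here.

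It may also be objected that leaving i(2) men out is itself an exclusion open only to PET-positive men. That is correct for specificity and PPV, and it is why the strict count is requested below. It does not affect pathology-only sensitivity, which uses pathology-positive men alone.

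**Conclusion.** The point holds on the text. Rule i(2) departs from the stated comparator and makes disease status depend on the read being judged. It can raise a reader's sensitivity and cannot lower it.

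The size cannot be fixed from the documents. In a borderline case one patient (45 diseased men) or two (61) move one reader across 65%; a reader at 60.0% of 45 would need seven. These figures rest on assumed values of k.

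This should be fixed because it governs the success criterion and costs little to correct. The documents do not show that it would decide the trial's outcome.

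**What to change.** In section 10.3.2 c):

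1. Base the sensitivity success decision on pathology at prostatectomy only, with i(2) patients left out of the numerator and denominator.
2. Report two named sensitivity analyses, with the number of i(2) patients per reader: (a) i(2) patients counted as true positives, as now; (b) i(2) patients counted as false positives, which is the strict pathology-only result for specificity and PPV.
3. In analysis (a), give a man whose retained node is proven diseased the same disease status for all three readers, so that a reader who called him negative scores a false negative.
4. State as a limitation that specificity and NPV still cannot detect residual disease in men whom all readers called negative.

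The cost is a paragraph and a table, with no change to imaging or surgery. A few patients leave the primary calculation, and sensitivity and PPV may look slightly less favourable. For PPV, assume 28 pathology-confirmed true positives, four i(2) patients and 10 other false positives: 32/42 = 76.2% now, 28/38 = 73.7% with the i(2) patients left out, and 28/42 = 66.7% under (b).

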- If there was a corresponding positive sclerotic lesion on the CT portion of the ⁶⁸Ga-PSMA-11 PET.

- If there is focal uptake seen on the baseline bone scan performed within one month of ⁶⁸Ga-PSMA-11 PET.

- If there is a lesion noted on the initial MRI performed within one month of ⁶⁸Ga-PSMA-11 PET.

- If within 12 months, follow-up CT demonstrates development of sclerosis.

- If within 12 months, follow-up MRI demonstrates a new bone lesion.

- If within 12 months, follow-up bone scan demonstrates new focal uptake.

(2) False positive:

- If ⁶⁸Ga-PSMA-11 positive bone lesions do not meet the criteria for true positive findings.

iv) Histopathology correlation: for lesions that have biopsy correlation, we will use the following criteria to determine positive and negative lesions:

(1) Positive HP/Biopsy: Confirmed sites of metastatic or tumor involvement by histopathology/biopsy will be discussed with the responsible physician/surgeon.

(2) Negative Biopsy: Patients with suspected tumor recurrence on ⁶⁸Ga-PSMA-11 PET with negative histopathology/biopsy will be handled as outlined below:

(a) Lymph nodes:

- For patients undergoing nodal dissection: Patients will be rescanned with dedicated CT or MRI to determine if the suspicious ⁶⁸Ga-PSMA-11-positive node was removed.

- If ⁶⁸Ga-PSMA-11 positive lymph node is still present, a repeat biopsy can be pursued if clinically feasible and applicable, or follow-up using imaging as described above will be performed.

- If the corresponding node was removed, then this will be considered a False Positive.
- For patients undergoing needle biopsy: Images of the procedure will be reviewed to determine if the correct node was biopsied.
 - If the correct node was biopsied, then a negative biopsy will be considered a False Positive.
 - If the incorrect node was biopsied, then follow-up imaging as described above will be performed.

(b) Bone lesions: Given the high rate of false negative biopsies for osseous metastases in patients with prostate cancer, patients with negative bone biopsies of ^{68}Ga -PSMA-11 PET-positive lesions will be further evaluated:

- If pathology demonstrates an alternative diagnoses that is known to be ^{68}Ga -PSMA-11-positive (eg, renal cell carcinoma (RCC) metastases; Paget's disease), then this will be considered a False Positive.
- If pathology is indeterminate, then follow-up imaging as described above will be performed to determine if the lesion is a True Positive or False Positive.

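### The primary false-positive rule accepts a node's absence on any post-prostatectomy scan, so a retained metastatic node that vanished on treatment before the rescan is scored a false positive

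*Combined protocol and SAP*

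**What the plan says.** All references are to the combined protocol and SAP.

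- **Section 10.3.2 c), iii)(1), false positive.** The rule reads: "PSMA-11 PET-positive for regional nodes; pathology at prostatectomy is negative; and imaging after prostatectomy demonstrates that node is no longer present". It gives no date for the imaging and does not mention treatment.
- **Section 10.3.2 c), i)(2), true positive.** For the same PET and pathology result, the patient is a true positive if "imaging after prostatectomy demonstrates node was not removed at surgery; and follow-up biopsy or imaging demonstrates presence of nodal disease".
- **Section 10.3.2 c), i)(2)(a).** This defines disease on follow-up: "Criteria for positive node on follow-up imaging: imaging within 3 to 12 months". One qualifying change is that "the node decreases by more than 30% (for patients undergoing systemic treatment or focal therapy at this site"). The window has no stated start point, and it governs the follow-up imaging, not the scan that decides whether the node was removed.
- **Section 10.3.2 c), v)(1).** A node shown to be retained, but without definitive follow-up, makes the patient non-evaluable.
- **Section 5.3, Clinical Follow-up a.i.** PET-positive, pathology-negative patients "will be rescanned with CT or MRI to determine if the suspicious node was thought to be removed". No timing is given.
- **Section 10.3.3 iv)(2)(a).** For nodal dissection: "Patients will be rescanned with dedicated CT or MRI to determine if the suspicious" node was removed. Then: "If the corresponding node was removed, then this will be considered a False Positive". Again no timing is given.
- **Section 10.3.3 i)(2).** For extra-pelvic nodes, a decrease of more than 30% is listed as a false positive only where there was no systemic therapy and no focal therapy at the site.
- **Section 3.2** restricts treatment before PET and surgery only. The study calendar in section 7 has no row for the rescan.

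**The concern.** Post-operative imaging has two jobs in the primary rules. It first shows whether the PET-positive node was taken out, and then, if the node was retained, whether it behaves like disease. Only the second job has a window. The first is answered in iii)(1) by absence alone, and absence has two possible causes: surgical removal, or response to treatment given after surgery. A scan taken after treatment has begun cannot tell them apart.

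The plan itself foresees post-operative treatment of a retained node, because i)(2)(a) has a criterion for it. Under that criterion shrinkage on treatment counts as evidence of disease. Under iii)(1) complete disappearance on the same treatment counts as evidence against disease, if it happened before the first post-operative scan. The class of a patient with a retained metastatic node can therefore depend on when he was scanned.

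Both co-primary measures are at stake. Each is judged as a point estimate against a fixed bar for each reader: 65% for sensitivity and 90% for specificity.

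**Working it through.** **1. The rules applied to one patient.** Take a man who is PET-positive and pathology-negative, with a retained metastatic node that disappears on post-operative treatment.

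| First post-operative scan | Later evidence | Rule | Class |
|---|---|---|---|
| Before treatment, node visible | Biopsy, or imaging at 3 to 12 months meeting the size criterion | i)(2) | True positive |
| Before treatment, node visible | No definitive follow-up | v)(1) | Non-evaluable |
| After the node has disappeared | None needed | iii)(1) | False positive |

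A reader who called the PET negative is unaffected: with negative pathology the patient is a true negative under ii)(1), whatever the rescan shows.

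**2. The plan's own figure.** Section 10.2.1 asks for 61 node-positive patients (45% against 65%, power 80%, alpha 0.01). A one-sample, one-sided normal approximation reproduces it:

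n = [(2.326·√(0.45·0.55) + 0.842·√(0.65·0.35)) / 0.20]² = 60.7, rounded up to 61.

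The expected yield sets the scale here: 200 × 0.75 = 150 operated; 150 × 0.30 = 45 pathology-positive; 150 − 45 = 105 pathology-negative. That 45 falls short of 61 is a separate matter.

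**3. One patient, reader close to both bars.** Of the 45 pathology-positive patients, 29 are true positives. The 105 pathology-negative patients are 94 true negatives, 10 genuine false positives and the patient in question. For simplicity, nobody falls under the wrong-region rule iii)(2).

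| Class given to him | Sensitivity | Specificity |
|---|---|---|
| True positive | 30/46 = 65.2% | 94/104 = 90.4% |
| Non-evaluable | 29/45 = 64.4% | 94/104 = 90.4% |
| False positive | 29/45 = 64.4% | 94/105 = 89.5% |

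**4. Several patients.** Let k of the 105 be such patients. The documents give no value; k = 0 to 5 is an assumption. TP is the number of true positives among the 45, and FP the number of genuine false positives.

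- Early scan with qualifying follow-up: sensitivity (TP + k)/(45 + k); specificity (105 − k − FP)/(105 − k).
- Late scan: sensitivity TP/45; specificity (105 − k − FP)/105.

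| k | Sensitivity, TP = 29: early / late | Specificity, FP = 10: early / late | Specificity, FP = 8: early / late |
|---|---|---|---|
| 0 | 64.4 / 64.4% | 90.5 / 90.5% | 92.4 / 92.4% |
| 1 | 65.2 / 64.4% | 90.4 / 89.5% | 92.3 / 91.4% |
| 3 | 66.7 / 64.4% | 90.2 / 87.6% | 92.2 / 89.5% |
| 5 | 68.0 / 64.4% | 90.0 / 85.7% | 92.0 / 87.6% |

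A reader with 8 genuine false positives stays above 90% with one late-scanned patient and drops below it with three.

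**The case against.** **Intent.** Sections 5.3 and 10.3.3 ask whether the node was removed, and i)(2) and v)(1) use the same idea. The phrase in iii)(1) can fairly be read as the counterpart of not removed at surgery. This stands as evidence of purpose. It does not cure the rule: the operative wording tests absence, and no section says when absence may be taken as removal. In 10.3.3 iv)(2)(a) the wording already turns on removal, so only the missing timing is at issue there.

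**A sure true positive.** A reader might infer that an earlier scan would always make this patient a true positive. The rules do not support that. Biopsy or qualifying imaging at 3 to 12 months is also needed, and otherwise v)(1) applies. It is also unclear whether the 3 mm minimum change applies to decreases.

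**A one-way bias against PET.** A reader might infer this too. It holds only if the node was metastatic. A benign node that shrinks on treatment after an early scan becomes a wrong true positive under i)(2)(a), while a late scan showing it absent gives the correct class.

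**A reversal of the trial.** A reader might infer that one late rescan would change the trial result. The example sits just above both bars, where any single reclassified patient would tip a reader, and success needs two of three readers. The 2-of-3 rule is only partial protection, however, because the rescan finding is common to every reader who called that node positive.

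**Rarity.** Several events must coincide: the node is missed although the urologist was told its location, all dissected nodes are negative, treatment starts before the rescan, and the node vanishes completely. This stands. No rate is given for any step, and zero such patients is possible.

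**Conclusion.** The point holds as a defect in a primary classification rule. As written, iii)(1) scores a retained metastatic node that disappeared on treatment before the rescan as a false positive. This conflicts with the rescan's stated purpose and with the plan's treatment of shrinkage on therapy in i)(2)(a) and 10.3.3 i). An earlier scan could have led to true positive or to non-evaluable.

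The size is unknown. With 45 node-positive and 105 node-negative patients, one such patient moves each measure by about one percentage point, which matters only for a reader close to a bar. The sensitivity bar equals the sensitivity assumed in section 10.2.1 (65%), so a reader near it is not a remote case. The documents do not support a claim that the trial's result would be reversed, or that the error always runs against PET.

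The conclusion rests on the plan's prevalence and surgery assumptions for scale, on the node being metastatic, and on an assumed number of such patients.

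**What to change.** 1. In 10.3.2 c) iii)(1), replace the test of absence with a test of removal at surgery. Accept absence on imaging as showing removal only when the scan was obtained before any post-operative systemic or pelvic treatment.
2. If treatment had already started when the node was found absent, classify the patient as non-evaluable in the primary analysis. Report sensitivity and specificity with these patients counted as true positives, and again as false positives.
3. State the start point of the 3-to-12-month window. Until that is done, a fixed post-operative deadline for the rescan cannot be placed before the window.
4. Use the last scan before treatment as the baseline for size change. If the rescan came after treatment began, that is the pre-operative scan. Section 3.1 already requires a diagnostic CT or MRI within 90 days of the PET. Using the rescan as baseline in every case would risk measuring change from a node that had already shrunk.
5. Apply the same condition to how removal is determined in 10.3.3 iv)(2)(a).

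This concerns classification and research-scan timing only; it does not direct or delay treatment. The rescan is already required, so the cost is a wording change, best made before outcomes are classified. The downside is that a few patients become non-evaluable.
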